5.9.1.4 Co-Dosing with CYP Inhibitors

Monitoring of circulating levels of F901318 is required when co-dosing with CYP inhibitors.

As F901318 is metabolized by CYP3A4 and CYP2C9 there is a potential for DDIs. Co-dosing with CYP3A4 inhibitors may increase exposure to F901318. *In vitro* data suggest that metabolism by other CYPs is limited. Consultation with the MM is advised if the combination of F901318 with a CYP3A4 inhibitor cannot be avoided.

Where use of concomitant medication has been approved, an extra visit for Unscheduled Trough PK sampling will occur 3 to 5 days after starting or stopping such concomitant medication. This Unscheduled Trough PK sample will be sent for rapid trough PK analysis of F901318, to support evaluation of the impact of the potential DDI.

The Unscheduled Trough PK samples will be sent to the regional hub for rapid trough PK analysis of F901318.

[REDACTED]

[REDACTED]

[REDACTED]

[REDACTED]

[REDACTED]

[REDACTED]

[REDACTED]

5.9.1.5 Co-Dosing F901318 with Sensitive and Moderately Sensitive CYP3A4 Substrates

Monitoring of circulating levels of the concomitant medication is required when co-dosing F901318 with sensitive and moderately sensitive CYP3A4 substrates.

F901318 is a perpetrator of potential DDIs with CYP3A4 substrates. As F901318 is a weak inhibitor of CYP3A4, co-dosing with sensitive and moderately sensitive CYP3A4 substrates may increase exposure of these substrates. Consultation with the MM and use of TDM for the substrate are advised if the combination cannot be avoided.

For those concomitant medications which are sensitive and moderately sensitive CYP3A4 substrates and which undergo routine TDM (such as transplant drugs), changes in concomitant drug treatment and all TDM results for the concomitant medication will be recorded. If the patient is receiving the concomitant medication prior to receiving F901318, a baseline TDM sample should be sent for analysis prior to F901318 treatment commencing. Further TDM sampling should be performed on a schedule based on the Investigator's judgment regarding the given medication.

Sensitive substrates: alfentanil, avanafil, budesonide, buspirone, conivaptan, cyclosporin, darifenacin, darunavir, dasatinib, dronedarone, ebastine, eletriptan, eplerenone, everolimus, felodipine, ibrutinib, indinavir, lomitapide, lovastatin, lurasidone, maraviroc, midazolam,

naloxegol, nisoldipine, quetiapine, ruxolitinib, saquinavir, sildenafil, simvastatin, sirolimus, tacrolimus, ticagrelor, tipranavir, tolvaptan, triazolam, and vardenafil.

Moderately sensitive substrates: alprazolam, aprepitant, atorvastatin, colchicine, eliglustat, pimozone, rilpivirine, rivaroxaban, tadalafil.

See also further guidance on sensitive and moderately sensitive CYP3A4 substrates at the FDA website.

5.9.2 Allowed Medications

See Section 5.9 for a general discussion of concomitant medications.

5.9.2.1 *Candida Prophylaxis and Concomitant Antifungal Therapy*

F901318 is not active against yeast infections and the use of fluconazole for prophylaxis or treatment of concomitant candidiasis is permitted at any time due to fluconazole's lack of activity against mould fungi. Patients who are receiving treatment with isavuconazole or posaconazole should be switched to receive treatment with fluconazole. Should a patient start or stop receiving fluconazole treatment whilst on study, an extra visit for Unscheduled Trough PK sampling will occur 3 to 5 days after starting or stopping such concomitant medication. This Unscheduled Trough PK sample will be sent for rapid trough PK analysis of F901318, to assess the impact of any dose adjustment made.

In order to meaningfully analyse the efficacy of F901318, it is important to avoid concomitant use of other systemic antifungal agents with known or potential activity against the primary fungal infection. That said, the constraints on choice of additional agents may be complex and thus use of any other systemic concomitant antifungal or combination treatment (such as addition of terbinafine for confirmed *Lomentospora prolificans* infections or an echinocandin to manage infection due to *Candida*) is permitted but is discouraged.

For all other infections, antifungal combinations should be based on the Investigator's clinical judgement with efforts made to minimize use where possible. Use of concomitant antifungal therapy must be discussed and agreed with the MM.

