	
5) Male patients with female partners of childbearing potential must either totally abstain from sexual intercourse or use a highly effective means of contraception throughout study participation and agree to continue its use for 30 days after stopping study drug.
 
6) Patients with confirmed Proven IFD (based on EORTC/MSG criteria) in the following categories*:
 
a) Lomentospora (Scedosporium) prolificans (LoPro),b) Scedosporium spp.,c) Aspergillus spp.,d) Other F901318-susceptible fungi (as described in the IB or based on information provided by the MM, and in either case requiring approval of the MM). 
OR with
 
e) Probable LRTD IA who meet the EORTC/MSG requirement for high risk host factor, clinical features and mycological criteria. 
*Enrolment is based on presumed F901318 susceptibility for categories a-c and selected other species as described in the IB. For IFD due to isolates from species of uncertain susceptibility, enrolment may occur with the approval of the MM before isolate susceptibility is confirmed. If an isolate is not available for shipping to the appropriate central lab for susceptibility testing, susceptibility will be predicted from species identification determined locally. If the isolate is subsequently found to be resistant, study therapy may be continued or discontinued based on clinical response at the discretion of the Investigator. Patients with infections due to multiple fungi can be enrolled provided at least one fungus is known or predicted to be F901318-susceptible AND the patient has limited alternative treatment options for that fungus as defined in Inclusion Criterion 7. As a specific example, a patient with simultaneous IA due to an azole-resistant strain and also invasive mucormycosis could be enrolled and treated with the combination of F901318 and isavuconazole. The choice of additional agents to treat other fungi should also consider the limitations applied to allowed medications. Cases of polyfungal infection should be discussed with the MM.
 
7) Patients will ALSO have limited alternative treatment options based on meeting one or more of the following criteria:
 
a) Known or predicted resistance of the infecting isolate to all licensed agents. LoPro automatically meets this criterion.b) Failure of available therapy. Failure to improve based on clinical or radiologic grounds despite receiving at least 7 days of standard antifungal treatment AND alternative licensed agents are either predicted to be ineffective or are contraindicated,c) Intolerance to available therapy. Current therapy cannot be continued due to therapy-related adverse reactions (e.g., increase in serum creatinine above ULN with an amphotericin, persistent visual disturbances with voriconazole, allergic reaction with any compound, or other recognized drug-related AE) AND alternative licensed agents are either predicted to be ineffective or are contraindicated,d) Inability to manage DDIs. Inability to continue current therapy due to DDIs that cannot be managed AND alternative licensed agents are either predicted to be ineffective or are contraindicated,e) Inability to produce therapeutic drug levels. Inability to produce or maintain therapeutic blood levels with current therapy AND alternative licensed agents are either predicted to be ineffective or are contraindicatedf) An IV-only option (e.g., an amphotericin) has produced a clinical response AND it is standard practice to switch to an oral azole for completion of therapy AND one of the following is true:

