
Concomitant Antifungal Therapy:
	
In order to meaningfully analyse the efficacy of F901318, it is important to avoid concomitant use of other systemic antifungal agents with known or potential activity against the primary fungal infection. The constraints on the choice of additional agents may be complex and thus use of any other systemic concomitant antifungal or combination treatment (such as addition of terbinafine for confirmed Lomentospora prolificans infections or an echinocandin to manage infection due to Candida) is permitted but is discouraged.
 
Antifungal combinations should be based on the Investigator’s clinical judgement and must be discussed with the MM.
 
Depending on the treatment given, an extra visit for Unscheduled Trough PK sampling (for rapid PK analysis of F901318) may be required 3 to 5 days after starting or stopping such concomitant medication, to support evaluation of potential DDIs.

Criteria for Evaluation:
 
Efficacy Endpoints:
 
Primary Endpoint:
 
 • DRC-adjudicated overall response rate by pathogen at Day 42. 
Secondary Endpoints (all by pathogen and also in aggregate)
 
 • DRC-adjudicated overall response at Day 7, Day 14, Day 28, main study phase EOT, Day 84 and 4-week FU. • Clinical response at Day 7, Day 14, Day 28, Day 42, main study phase EOT, Day 84 and 4-week FU. • Where appropriate for the IFD, radiological response at Day 7, Day 14, Day 28, Day 42, main study phase EOT, Day 84 and 4-week FU. • Mycological response by pathogen and by susceptibility category at Day 7, Day 14, Day 28, Day 42, main study phase EOT, Day 84 and 4-week FU. • Investigator-assessed overall response (integration of clinical, radiological, and mycological response) at Day 7, Day 14, Day 28, Day 42, main study phase EOT, Day 84 and 4-week FU. • All-cause mortality at Day 42, main study phase EOT, Day 84 and 4-week FU. • Quality of life (patient-reported outcome) [REDACTED], based on the EQ-5D-5L questionnaire. 
Note: For patients who will receive ET beyond Day 90, the Day 84 visit and the main study phase EOT visit will be combined into a single Day 84/EOS/EOT visit on approximately Day 90. Subsequent visits [REDACTED] to assess the safety of continued treatment and to assess the need for further treatment, and there will be a FU visit 4 weeks after ET is completed.
 
Safety:
	

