2.1.2 F901318 has potential to address that unmet need

F901318, also known as 2-(1, 5-dimethyl-3-phenyl-1H-pyrrol-2-yl)-N-{4-[4-(5-fluoropyrimidin-2-yl) piperazin-1-yl]-phenyl}-2-oxo-acetamide, is the first of a new class of antifungal agents. F901318 has a novel, well defined mechanism of action, inhibiting a rate limiting enzyme of fungal pyrimidine biosynthesis, DHODH. F901318 potently inhibits fungal DHODH but is a very poor inhibitor of the human enzyme. This differential activity is consistent with the differences in structure between the human and fungal DHODH enzymes.

As discussed in the Nonclinical Pharmacology section of the IB, F901318 is active against a wide range of *Aspergillus* species including those most commonly associated with human infection. Importantly, F901318 is effective against isolates of *A. fumigatus* resistant to other antifungal agents, *Scedosporium* spp. and *Lomentospora prolificans*; the latter is frequently refractory to all available antifungal agents. F901318 is also active against a range of other

filamentous fungi with the notable exception of the zygomycetes. F901318 has no activity against yeasts, zygomycetes, and some *Fusarium* species.

Within F901318's spectrum of activity is an evolving panel of other "uncommon" moulds which are typically resistant to the azole antifungals and/or polyenes, including *Rasamsonia* species as well as *Acremonium*, *Scopulariopsis*, *Microascus*, and *Paecilomyces* species. Treatment with F901318 may be of benefit in these IFDs, particularly in patients unable to tolerate alternative treatment options.

Sustained exposure to F901318 is lethal to fungi. Vacuolation, cell wall thinning, and cell wall rupture are seen. Loss of cell membrane integrity can be shown by viable dye exclusion studies.

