- a) *Lomentospora (Scedosporium) prolificans* (LoPro),
- b) *Scedosporium* spp.,
- c) *Aspergillus* spp.,
- d) Other F901318-susceptible fungi (as described in the IB or based on information provided by the MM, and in either case requiring approval of the MM),

OR

- e) Probable LRTD IA based on EORTC/MSG criteria (Appendix 2) but not meeting the criteria for culture proven invasive fungal infection.

*Enrolment is based on presumed F901318 susceptibility for categories a-c and selected other species as described in the IB. For IFD due to isolates from species of uncertain susceptibility, enrolment may occur with the approval of the MM before isolate susceptibility is confirmed. If an isolate is not available for shipping to the appropriate central lab for susceptibility testing, susceptibility will be predicted from species identification determined locally. If the isolate is subsequently found to be resistant, study therapy may be continued or discontinued based on clinical response at the discretion of the Investigator. Patients with infections due to multiple fungi can be enrolled provided at least one fungus is known or predicted to be F901318-susceptible AND the patient has limited alternative treatment options for that fungus as defined in Inclusion Criterion 7. As a specific example, a patient with simultaneous IA due to an azole-resistant strain and also invasive mucormycosis could be enrolled and treated with the combination of F901318 and isavuconazole. The choice of additional agents to treat other fungi should also consider the limitations applied to allowed medications (Section 5.9.2). Cases of polyfungal infection should be discussed with the MM.

7. Patients will also have limited alternative treatment options based on meeting one or more of the following criteria:

- a) **Known or predicted resistance of the infecting isolate to all licensed agents.** LoPro automatically meets this criterion – other fungi may qualify after discussion with the MM,
- b) **Failure of available therapy.** Failure to improve based on clinical or radiologic grounds despite receiving ≥ 7 days of standard antifungal treatment AND alternative licensed agents are either predicted to be ineffective or are contraindicated,
- c) **Intolerance to available therapy.** Current therapy cannot be continued due to therapy-related adverse reactions (e.g., increase in serum creatinine above upper limit of normal

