6.3.1 Investigator's Assessment of Overall Response

Diagnostic assessments used to support the Investigators assessment of response include mycological culture, histology/cytology, GM, PCR, other mycology assessments, bronchoscopy and radiology tests used to confirm enrolment of the patient. It is essential, where possible, that the same methods are used for both diagnosis and assessment of overall response. Any additional assessments performed during the course of the study to assess the patients status may also be used to support efficacy response assessments.

The Investigator's assessment of response will be recorded at Day 7, Day 14, Day 28, Day 42, Day 84/EOT main study phase and 4 weeks after EOT in the main study phase. The Investigator will provide his/her opinion of the patient's response, based on the efficacy criteria as described in Section 6.3.1.1 (clinical), Section 6.3.1.2 (radiological), Section 6.3.1.3 (bronchoscopic), Section 6.3.1.4 (mycological) and Section 6.3.1.5 (overall response).

For patients who receive ET with F901318, the Investigator's assessment of overall response will be recorded at each visit to support continued treatment.

If multiple fungal mould pathogens are present, the DRC will separately analyse outcome for each relevant pathogen. Pathogens which were known at baseline to be F901318-resistant and for which alternative concomitant therapy was provided are not separately scored by the DRC. For example, a patient treated with F901318 and isavuconazole for simultaneous azole-resistant aspergillosis and mucormycosis would receive an overall score only for the response of the aspergillosis. As appropriate, the Investigator may provide per-fungus comments on the clinical, radiological, and mycological elements but per-fungus scores for each of these sub-elements are not required.

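### The instruction in Protocol Section 5.9.2.1 to switch isavuconazole or posaconazole to fluconazole states no exception for the F901318 plus isavuconazole regimen that the protocol itself describes

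*Protocol*

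**What the plan says.** Section 5.9.2.1 covers Candida prophylaxis and concomitant antifungal therapy. Its first paragraph allows fluconazole at any time for preventing or treating candidiasis, on the ground that fluconazole does not act on moulds. The next sentence reads: "Patients who are receiving treatment with isavuconazole or posaconazole should be switched to receive treatment with fluconazole". The rest of the paragraph deals with trough sampling when fluconazole is started or stopped.

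Three other places describe a patient on isavuconazole:

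- Inclusion Criterion 6, in the Synopsis and again in Section 4.3.1, gives the example of azole-resistant invasive aspergillosis with simultaneous invasive mucormycosis. Such a patient "could be enrolled and treated with the combination of F901318 and isavuconazole".
- Section 4.3.1 follows the example with a cross-reference: "The choice of additional agents to treat other fungi should also consider the limitations applied to allowed medications (Section 5.9.2"). It then adds: "Cases of polyfungal infection should be discussed with the MM".
- Section 6.3.1 uses the same case, "a patient treated with F901318 and isavuconazole for simultaneous azole-resistant aspergillosis and mucormycosis", to illustrate a scoring rule for the Data Review Committee (DRC): "Pathogens which were known at baseline to be F901318-resistant and for which alternative concomitant therapy was provided are not separately scored by the DRC".

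On spectrum, Section 2.1.2 states that "F901318 has no activity against yeasts, zygomycetes" and some Fusarium species.

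**The concern.** A site that enrols the example patient and follows the cross-reference in Criterion 6 arrives at a sentence that, taken at its word, tells it to stop the isavuconazole that the example prescribes. Concomitant antifungal treatment is an operative rule. Section 7.0 asks investigators not to depart from the protocol without approval, apart from immediate hazards and logistical or administrative changes, and up to 100 centres are planned. Written treatment rules should therefore agree with each other.

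What is at stake is the care of one kind of patient, whom the protocol foresees by name. No estimate or test is involved. If the sentence were applied to that patient, the drug directed at the second mould would be replaced by one that the same paragraph describes as inactive against moulds.

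**Working it through.** No arithmetic applies, so the check sets the texts side by side.

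1. **Who the switch sentence covers.** It covers patients receiving isavuconazole or posaconazole. It is not limited by pathogen, by prophylaxis versus treatment, or by reason for use. Exceptions stated in the sentence: none.

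2. **Whether the example patient is covered.** The patient in Criterion 6 and Section 6.3.1 receives isavuconazole, so on a literal reading the answer is yes.

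3. **What is left after the switch.** The patient would be on F901318 and fluconazole. Section 2.1.2 rules out F901318 activity against zygomycetes. The sentence just before the switch instruction rules out fluconazole activity against moulds. Neither drug would act on the Mucorales infection.

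4. **Whether the combination is meant only for the moment of enrolment.** It is not. Section 6.3.1 tells the DRC how to score response when a baseline pathogen known to be F901318-resistant has its own concomitant therapy. That rule presupposes that the second drug is given on study.

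5. **Whether another sentence in Section 5.9.2.1 works as the exception.** The second paragraph warns that "it is important to avoid concomitant use of other systemic antifungal agents with known or potential activity against the primary fungal infection", and then allows other systemic antifungals or combinations while discouraging them. That allowance is written as a relaxation of the warning about the primary infection. The third paragraph leaves combinations for other infections to the Investigator's judgement and requires MM agreement to any concomitant antifungal. Both paragraphs point towards keeping isavuconazole, but neither refers to the switch or says when it is waived.

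6. **What the redactions allow.** The switch sentence and its paragraph are fully visible. Section 5.9.1.4, on CYP inhibitors, is heavily redacted. Section 6.5 points there for sampling requirements with other antifungal drugs, yet the visible part names none. Azole guidance may lie in the hidden text, so nothing is inferred from its absence.

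Result: for the example patient, the literal switch instruction and the literal example cannot both be followed. The other text in the section makes the intended answer fairly clear but does not state it.

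**The case against.** The strongest reply is that the conflict appears only when one sentence is taken out of its paragraph. The sentences on either side concern fluconazole for yeast cover, so the natural purpose is to replace mould-active azoles that are no longer needed once F901318 is started. The wording is advisory. The rest of the section allows combinations and leaves them to clinical judgement, and mucormycosis falls under the other infections that it mentions. A specific named example should also prevail over a general instruction. The amendment history in Appendix 4 records that the isavuconazole example and new text in the second paragraph of Section 5.9.2.1 both came in with Amendment 03, which suggests that they were considered together. Finally, the MM stands between the sentence and any action, and Exclusion Criterion 4 asks for urgent follow-up of Mucorales.

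Most of this stands. It shows what was probably meant and why harm is unlikely. It does not supply the missing words: the section heading also covers concomitant antifungal therapy in general, and the switch sentence is not confined to yeast cover.

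Two stronger readings should be set aside:

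- A reader might infer that the protocol forbids the combination, or contradicts itself beyond repair. The Candida context, the later paragraphs and the MM requirement do not support that.
- A reader might see a second discrepancy in the Synopsis, whose section on concomitant antifungal therapy lacks the switch sentence. The Synopsis leaves out the whole fluconazole paragraph, which is ordinary condensation and, if anything, supports reading the sentence as part of the Candida advice.

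**Conclusion.** The point holds as a minor internal inconsistency in a treatment rule. It rests on the literal wording of the switch sentence, on the protocol's own statements about the spectrum of F901318 and fluconazole, and on visible text only. Related guidance in the redacted part of Section 5.9.1.4 could reduce its practical importance further.

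Its size cannot be expressed in patients. The documents give no number with mould co-infection and none receiving isavuconazole or posaconazole, so any count would be invented. A reader might also infer that patients were left untreated or that efficacy results are affected. The documents support neither: several written safeguards protect this patient, and sample size, endpoint definitions, data collection and analysis do not depend on the sentence.

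**What to change.** Keep the sentence in Section 5.9.2.1, but limit it to isavuconazole or posaconazole given for yeast prophylaxis or treatment, or for the primary mould infection. Then add:

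*This does not apply when isavuconazole or posaconazole is given, with MM agreement, to treat a concurrent F901318-resistant mould infection as described in Inclusion Criterion 6 and Section 6.3.1.*

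The cost is one qualifier and one added sentence. The requirement for MM agreement is kept. Concomitant antifungals are already recorded under Protocol Section 5.9 and summarised under SAP Section 12, so neither the case report form nor the analysis changes.
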